4.19. Stratégie Avancée and field workers' assessment of hard-to-reach areas

Villages under Stratégie Avancée will be identified by the local field supervisors from the records maintained by the local districts and health areas. The Stratégie Avancée status information will be appended to the study data prior to the analysis by the study data manager.

We will conduct a survey amongst the trial data collection staff to obtain a subjective assessment on what is the geographical accessibility of a village. The overarching aims of the survey for the data collectors would be to develop an instrument to assess the hardness-to-reach from the point of view of data collectors or health care workers going to the locations, and to evaluate whether hardness-to-reach modify the effectiveness of LAKANA intervention. The survey will be implemented as an electronic questionnaire and the survey will be anonymous: no staff name or position will be recorded.

The participants will be approached by their field supervisors with an announcement of an invitation to fill the questionnaire based on their own experiences. Filling the questionnaire will be voluntary, but they will be informed on the benefits of what such information can provide: insight on their challenges during the data collection, an improved viewpoint on the collected trial data with hardness-to-reach as a predictor or effect modifier on the trial outcomes, and information that could improve the planning of future interventions that could help even the most remote communities.

The participants will be asked to fill the questionnaire before synchronizing the tablets for data collection, either at the beginning of the day or at the end of the day, at their convenience. The questions will be in French language, and at the beginning of the questionnaire, there will be a brief introduction and instructions on filling the electric form.

The form will consist of 12 questions for a single village. Each field worker will fill the form for 10 villages. The questions will be multiple choice questions and filling the form for one village will take approximately 5 minutes.

The expected number of answers will be 75% of the available field workers. The field supervisors will be reminded to ask the field workers to fill the form until 75% is reached, or until the field supervisors report that there are no more field workers who are willing to fill the form. As the data collectors enter villages in teams, there are multiple data

collectors who have experience from a single village. Each village should be assessed by the full team of field workers, that is, each village should have at minimum two assessment by separate field workers.

There will be multiple survey rounds: the survey will be tested with 5 data collectors to assess the workload filling the forms for multiple villages, and to assess the data quality. If the data quality suffers from the workload of filling the questionnaire for many villages, the length of the electronic data capture form will be reduced by allowing the field workers to continue form filling at the later time.

4.20. Data collection on trial safety

We will monitor intervention safety in LAKANA with two approaches:

1. Passive surveillance for the incidence of serious adverse events (SAE) within 14 days of study drug administration, in the whole study area
2. Active surveillance for the incidence of SAEs and adverse events (AE) within 14 days of study drug administration, in the 60 villages selected for more detailed data collection on outcomes other than mortality.

The passive surveillance will be done through health facilities in the study area. Whilst an MDA round is being implemented in any location and for two weeks thereafter, a study coordinator will visit or call the local health center on each week-day and record any suspected SAEs that have been notified among 1-11 month old infants at the facility. Caregivers of infants who receive study drugs are also advised to notify study team members if the infant is hospitalised within two weeks of the MDA.

The following events will be considered SAEs, if they occur within 14 days of study drug administration: Death, life-threatening event, hospitalization, and other serious events as judged by a study physician.

Active surveillance for SAE and AE will be completed for participants in the 60 clusters selected for more detailed data collection on a number of secondary outcomes and other variables. Infants aged 4-11 month old will be invited to the health facilities or central location in a village two weeks after the 4th round of MDA has been conducted in their communities. At this visit, a study nurse or another trained study team member will also interview a caregiver about symptoms that the infant has experienced after the azithromycin MDA and that may possibly be related to it.

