 - b. Earlier research has shown that AMR prevalence will increase among treated individuals. How and if this prevalence persists in these treated children 1 year after their treatment has finished but the villages they live in are still on MDA intervention is currently not known. We will assess phenotypic macrolide resistance and resistance against other antibiotics categorized by the World Health Organization (WHO) into "Access" group and/or that may have overlapping mechanisms: meropenem, ceftriaxone, ciprofloxacin, ampicillin, co-trimoxazole, and gentamicin for *E.coli*, and oxacillin, erythromycin, vancomycin, ciprofloxacin, ampicillin, co-trimoxazole for *S. pneumoniae*.
 - c. We will assess genotypic markers of resistance and changes in the intestinal microbiome in children previously treated with azithromycin and we expect that the microbiome in these children has recovered 1 year post treatment and is similar to the microbiome of children in the placebo group.

Outcomes related to the mechanism of azithromycin activity

1. Blood C-reactive protein concentration
2. Blood malaria parasitemia, and hemoglobin concentration
3. Fecal neopterin, myeloperoxidase, and alpha-1-antitrypsin concentrations

Safety outcomes:

1. Incidence of serious adverse events (SAE) within 14 days of study drug administration.
2. Incidence of adverse events (AE) within 14 days of study drug administration.

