4.12. Data collection on infant and child mortality

At the enrollment visit, a data collector hired by the the study team will interview a household head to collect information on household composition. S/he will record the household members in a password-protected and encrypted electronic trial database, to which s/he can refer to and which s/he will update during subsequent visits. The database will include the following information on each member of the household: Sex, name, date of birth, age, date of start of follow-up (enrollment of household or in-migration), date of end of follow-up (death, withdrawal, or out-migration)

At each of the subsequent visits, the data collector will check the vital status (alive, dead, out-migrated, or unkown) of the previously registered household members and record any new births and in-migrations. If a child death - is noticed, there will be a special set of questions on the date and cause of death. Cause of death will be classified into trauma, acute illness of less than two weeks duration, prolonged illness of more than two weeks of duration, or other, i.e. no extensive verbal autopsies or other cause of death ascertainment will be done. Valid vital status information can be obtained from a parent or other caretaker of the child who lives in the same household; if such a person is not available, the information will be considered missing.

Mortality will be expressed as deaths / 1000 years at risk. Each 3-month interval will contribute to mortality calculation. Children will be included in the analyses if they were present in the household at the beginning of the interval and their vital status (dead or alive) was known and provided to the study team at the subsequent visit, by an eligible adult (see above for eligibility criteria). Time in follow-up will be the number of days between the beginning of the interval and death, outmigration, or end of interval, whichever came first. All mortality data i.e. from both the primary outcome sample and the secondary outcome sample will be used for the primary mortality outcome analysis.

Mortality rates will be calculated separately for 29-364 days old infants (the primary target population for the intervention) and for 12.00-59.99 month old children (who have not themselves received the MDA intervention). The indicated figures refer to the subject's age at the beginning of the interval.

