6.08. Data safety and monitoring board (DSMB)

A review board will be constituted prior to commencement of the study to oversee the progress and assess the safety of the intervention. The trial team will provide the DSMB members a monthly summary of trial progress and documented and expected numbers of serious adverse events (SAEs).

The DSMB will meet in person before the trial onset and conduct thereafter scheduled electronic meetings 1-2 times a year, to discuss the progress and safety data. Additionally, any member of the DSMB may request an additional meeting at any point.

As part of the adaptive design, there will be a planned interim data analysis, as explained in chapter 4.13. In case of any unusual events, members of the DSMB may request additional interim analyses at their discretion.

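### Death within 14 days of a dose is an SAE, but the plan does not say that deaths dated by the census in that window enter the SAE outcome or the monthly DSMB numbers

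*Combined protocol and SAP*

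**What the plan says.** Section 4.07 lists as safety outcome 1: "Incidence of serious adverse events (SAE) within 14 days of study drug administration". Section 4.20 gives the qualifying events as "Death, life-threatening event, hospitalization, and other serious events as judged by a study physician", with no condition on where a death takes place. Section 4.08 says SAE data come from all 1150 villages.

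The capture routes are:

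- **Health facilities, whole area (4.20).** "The passive surveillance will be done through health facilities in the study area". During an MDA round and for two weeks after it, a coordinator contacts the local health centre each weekday to "record any suspected SAEs that have been notified among 1-11 month old infants at the facility".
- **Caregivers, whole area.** In 4.20 they are "advised to notify study team members if the infant is hospitalised within two weeks of the MDA". Section 4.11 adds general advice, given at dosing, to contact the team about anything out of the ordinary.
- **Active surveillance, 60 villages (4.20).** The procedure described is a single visit: "Infants aged 4-11 month old will be invited to the health facilities or central location in a village two weeks after the 4th round". The caregiver is then interviewed about symptoms since the dose.

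Separately, section 4.12 has the quarterly census check vital status. When a child death comes to light, "there will be a special set of questions on the date and cause of death". Vital status is treated as missing if no eligible caretaker from the household can be found.

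Section 6.08 gives the DSMB a monthly summary that includes "documented and expected numbers of serious adverse events (SAEs". Section 5.03 adds one interim safety analysis alongside the interim efficacy analysis.

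**The concern.** The SAE definition takes in all deaths in the window, but the written capture routes need someone to come forward: a facility, or a caregiver who contacts the team. An infant who dies at home in the second week after a dose, and whose family does not call, reaches the trial only through the next census visit. That visit supplies a date of death. Doses are given at the same quarterly visits and all data are captured electronically (4.27), so the interval from dose to death can be computed. Yet none of 4.12, 4.20, 5.03, 6.08 or 6.09 says that it is computed, or that the result counts as an SAE.

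What is at stake is the completeness of safety outcome 1 and of the DSMB's routine safety numbers, for the gravest and least ambiguous kind of SAE. Safety outcome 1 is also the only written outcome that would show an excess of deaths soon after dosing separately from the rest of the 3-month interval.

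**Working it through.** **1. Reproduce the base.** Section 5.04 gives 35,650 infants with follow-up at each of six rounds, 28,520 at the 7th and 17,820 at the 8th:

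6 × 35,650 + 28,520 + 17,820 = 260,240, against about 260,200 stated. The figure reproduces.

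**2. Person-time in the 14-day windows.** 260,200 × 14 / 365.25 = 9,973 person-years.

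**3. Expected deaths in those windows.** Inputs from 5.04 are 20, 16 and 12 deaths per 1000 person-years for control, azi-biannual and azi-quarterly, with clusters in the ratio 3 : 4 : 2. The hazard is assumed constant across the interval.

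- Control: 9,973 × 3/9 × 0.020 = 66.5
- Azi-biannual: 9,973 × 4/9 × 0.016 = 70.9
- Azi-quarterly: 9,973 × 2/9 × 0.012 = 26.6
- Total: 164

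The arm-weighted rate is (3×20 + 4×16 + 2×12)/9 = 16.4 per 1000. Taking each interval as a quarter of a year, deaths over all intervals are 260,200 × 0.25 × 16.44/1000 = about 1,070, so the windows hold about 15% of them.

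**4. Dosed infants instead of analysable infants.** Section 5.04 has 34 dosed per cluster and 31 found at the next visit. Scaling by 34/31 gives 164 × 34/31 = about 180 deaths. A census that finds 31/34 (91%) can date about 164 of these. At the 80% ascertainment expected in 4.10 it could date 0.80 × 180 = about 144. This assumes the same mortality in infants who are not found.

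**5. Does active surveillance close the gap?** Section 4.17 expects about 1,000 infants at the fourth-MDA visit; an upper figure is 60 × 31 = 1,860.

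- Share of intervals: 1,000/260,200 = 0.4%; 1,860/260,200 = 0.7%
- Expected 14-day deaths among them: 1,000 × 14/365.25 × 16.44/1000 = 0.6; for 1,860 infants, 1.2

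It does not.

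**6. Deaths that could go uncounted.** The documents give no share of deaths that neither a facility nor a caregiver reports. As an assumption:

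- 25% unreported: 0.25 × 164 = 41
- 50%: 82
- 75%: 123

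**7. Does the primary outcome show the same thing?** Illustration, again with a constant baseline hazard: suppose mortality doubled in the first 14 days and was 20% lower for the rest of the interval. The interval-wide rate ratio would be 0.153 × 2 + 0.847 × 0.8 = about 0.98. A pooled 3-month analysis would look null while the 14-day window showed a doubling.

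**The case against.** The strongest reply is that the plan is silent on the link but does not exclude it. The SAE definition has no restriction on place or source, 6.08 does not say where the documented counts come from, and operating procedures outside the protocol may already make the link. That is fair: loss of these deaths is a consequence of following the text as written, not something the text prescribes.

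Several stronger readings are tempting and should not be adopted:

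- *Facilities and calls about hospitalisation are the only routes.* Section 4.11's general advice to caregivers would cover a death, and there is the active visit. The advice does not name death or set up a recording step.
- *The census has every death.* Section 4.12 allows missing vital status, and 4.10 expects it to be known for about 80% of dosed infants.
- *The DSMB never sees home deaths.* Those found by the census are in the primary outcome and in the interim mortality data. The harm rule in 6.09 covers increased mortality, and the DSMB may ask for further analyses. What stands is that only one interim analysis is scheduled and that the mortality outcome pools 3-month intervals.
- *Documented SAEs must fall below expected SAEs.* The plan does not say how the expected number is derived; it may already allow for passive capture.
- *Capture differs between arms.* The trial is randomised and double-masked, and nothing in the documents points to differential reporting.
- *The facility log omits infants who turn 12 months inside the window.* The 1–11 month label is the protocol's usual name for the dosed population, defined by age at dosing, so this reading is too literal to press.

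**Conclusion.** The point holds as a gap between the SAE definition and the written means of capturing it. Outside one visit covering under 1% of intervals, SAE capture rests on facility notification and caregiver reports. No section states that census deaths dated within 14 days of a dose are added to safety outcome 1 or to the monthly DSMB numbers. Unreported home deaths can therefore be missing from both, while still counting towards mortality.

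About 164 deaths are at issue (66 control, 71 azi-biannual, 27 azi-quarterly), resting on the planning rates in 5.04 and a constant hazard. The range of 41–123 omitted rests on an assumed 25–75% unreported and is an illustration, not an estimate from the documents. The primary efficacy analysis is unaffected. The sponsor should make the change because the safety outcome is otherwise incomplete for deaths and the data to complete it are already being collected.

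**What to change.** - In 4.20, state that in all villages a database query flags any census death dated within 14 days after that child's recorded dose, and that each flagged death counts in safety outcome 1.
- In 6.08, state that these deaths are included in the DSMB summaries, labelled as late-identified so that they can be told apart from events reported at the time.
- In the caregiver message in 4.20, name death as well as hospitalisation as a reason to notify the team.

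The cost is one query and a few sentences, with no new visits or staff. There are three downsides. Deaths found this way can arrive up to about 3 months late, so the outcome becomes more complete but reporting does not become prompt. Deaths in households with no eligible informant stay missing. The reported SAE incidence will be higher than under facility and caregiver reports alone, which the safety report should explain. If the sponsor intends to leave census deaths out, 4.20 should say so and be reconciled with its own definition of an SAE.

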4.21. Group allocation and trial code management

Participating study clusters (villages) will be randomly allocated into the three intervention groups at 3:2:4 ratio (control: azi-quarterly: azi-biannual), in public allocation events where village representatives blindly pull lottery tickets out of a container. The randomization will be stratified by cluster size (below or above 100

infants / cluster) and by district, i.e., each participating district will have its own randomization event. The randomization lists (trial code) will be stored electronically, in a password protected file, by a statistician not involved in trial implementation, the data management consulting company, and by the Chairman of the trial's data safety and monitoring board (DSMB).

The trial code will be opened when all trial data for the 24-month follow-up visit have been entered into a computer database and data accuracy has been verified. To facilitate an analysis on mortality and other efficacy outcomes whilst follow-up for AMR is still going on, a statistician will temporarily break the code, add group information to a database containing the efficacy outcomes and then recode participant and cluster codes into new identifiers that cannot be linked to the actual identification. With this approach, the statistician can then share a full database with researchers analysing the efficacy outcomes, whilst others continuing the data collection of AMR outcomes will remain blinded to the group code.

4.22. Methods for protecting against other sources of bias

Randomisation into the trial, group allocation, and distribution of study drugs will be done by personnel not participating in the outcome evaluation.

The interventions will be double-masked, i.e., the study drugs will look and taste identical and coded only with a letter code.

To ensure adherence, all study drugs are given under direct observation.

4.23. Withdrawal from participation after enrollment

The enrolled household representatives can decide to discontinue the study participation or decline provision of study drug to an infant at any point. If known, the reason for household withdrawal or study drug denial will be indicated in electronic Case Report Forms. The participants can, however, withdraw their consent or decline study provision to a child without giving any reason for their withdrawal.

Individuals experiencing a serious adverse event that is likely to be related to the trial intervention are withdrawn from further study drug provision by the investigators (but will be included in the follow-up and analysis).

Withdrawn or discontinuing participants will not be replaced by others, i.e. possible dropouts will not influence the sample size, once the study has started. The study team will compare the baseline characteristics of discontinuing households to those who do not discontinue, in order to assess the possibility of follow-up bias.

4.24. Other treatments to trial participants

During and after the trial, members of all participating households (i.e., those completing the planned follow-up period as well as those withdrawing at some point) will receive standard preventive and curative health services, as recommended and provided by the national health system. SMC with amodiaquine and sulfadoxine-pyrimethamine will be offered through the national health service to all 3–59-month-old children on a monthly basis between July and October–November in each year.

At the end of the trial, if the analysis suggests a mortality reduction by azithromycin, all 1–11 month (29–364 days) old infants in the participating households will be offered a 20 mg / kg dose of azithromycin. If deemed appropriate thereafter, the study team will work with Malian Ministry of Health to roll-out a longer-term azithromycin MDA program at the trial site and elsewhere in Mali.

4.25. Co-enrollment guidelines

LAKANA trial participants are encouraged not to enrol in other clinical trials using antibiotics before the end of the LAKANA follow-up period. However, participation in or enrollment to another trial is not an exclusion criterion, i.e. child can be included in the trial and receive study drug MDA if s/he was participating also in another trial.

4.26. Storage of biological samples

All collected biological samples will originally be shipped daily to study laboratory in Kita, where they will be processed and stored at a project freezer (-80°C). On a monthly

basis, the samples will be shipped to a main laboratory at CVD-Mali in Bamako and stored at -80°C. All biological samples will be aliquoted in small volumes, to allow appropriate vials to be easily shipped to various collaborators, where they will be stored until analysis. Chapters 4.15 and 4.16 gives details of the stored aliquots.

4.27. Data recording and management

All data will be captured electronically, using a custom-made data entry software installed on personal smartphones or small tablet computers. The exact software is yet to be decided but the data management approach will involve offline data collection, mostly at participant's home. Data transmission to a cloud-based server will occur in real-time from households in the field or daily from cluster centers, using a 3G broadband connection. All server-based data will be backed up to another location daily.

Access to the tablet computers and the cloud-based data will be username and password protected. During transmission and at the cloud, data will be encrypted to ensure data privacy. The tablet computers will be stored and charged overnight at locked study offices that will have safety and electricity.

Error and inconsistency checks will be automated in the software. A data manager will review new data entries and full data report on a weekly basis (daily at the beginning of data collection) and make corrections where appropriate, to ensure data integrity.

All documentation regarding the participants, including the laboratory samples, source data and the Case Report Forms, will be identified in the database with appropriate participant codes. The names will only appear on informed consent forms and a separate coding list. A minimal set of identifying information, necessary for the implementation of the trial, will be stored in an encrypted form on the data collection devices and in a separate encrypted database. Access to the identifying information will be limited to authorised data collectors with a secure username and password.

The investigators shall maintain electronic records of study drug receipts and transfer logs and electronic copies of the Case Report Forms and regulatory documents (informed consents, ethical approval) for 5 years after the end of the study, as advised by local authorities. All records will be kept in a secure place. Clinical information will not be released without written permission of the subject, except as necessary for monitoring.

Selected data (participant's name, sex, date of birth, date of last visit, home village, household identification number, enrollment date and enrollment number) will be summarised in an electronic register. The registers are stored in encrypted form and accessible only with an authorised username and password in the data collectors tablet computers (to facilitate participant identification) and a cloud-based folder. Data from this register may be given to selected members of the research teams and authorities guiding health research in Mali or Finland.

After the trial completion, the study team will place the study database and respective metadata publicly available, at a suitable non-profit internet-site (such as ClinEpiDB).

The study team will contract an external partner (RTI International) for the development of the data entry and management system support for its maintenance. After the initial 14 months, i.e. when the system is running and enrollment almost completed, the study team will assume full responsibility of data management.

